### **3.9 Safety Analyses**

All safety analyses will be performed based on SAF set. There will be no statistical comparison between treatment groups for safety data except hypoglycemic events.

All sub-sections below will be listed for SAF set.

#### **3.9.1 Adverse Events (AEs)**

An adverse event is the development of an undesirable medical condition or the deterioration of a pre-existing medical condition following or during exposure to a pharmaceutical product, whether or not considered causally related to the product.

AEs will be collected on CRF form “pAE” from the first dosing day to EOT visit, and all recorded AEs will be reported in tables and listings.

Adverse Events (AEs) will be coded using the MedDRA central coding dictionary, Version 20.0. The terms not yet coded in the data management transfer will be summarized in the ‘Uncoded’ category.

Pre-existing conditions will be recorded at baseline on Medical History page of CRF. If a pre-existing condition changes in severity, it will be reported as an AE. If a persistent AE becomes more severe, it should be recorded again with the updated severity.

An overall summary of number of patients within each of the categories described in the sub-section below, will be provided as specified in the output templates. The focus of adverse event reporting in result tables will be based on Treatment Emergent Adverse Events (TEAEs).

Incidence of AEs will be presented by System Organ Class (SOC) and Preferred Term (PT) and also broken down by maximum intensity and relationship to study medication. In the case that a patient reports multiple AEs within the same category, the AE with worst severity and strongest relationship will be used in the corresponding summaries.

### **3.9.1.1 Intensity**

The patient (parents/legal guardians) will be asked to assess the maximum intensity of the reported AEs according to the following scale:

- Mild (awareness of sign or symptom, but easily tolerated)
- Moderate (discomfort sufficient to cause interference with normal activities)
- Severe (incapacitating, with inability to perform normal activities).

An AE with missing severity grade will be considered as Moderate.

### **3.9.1.2 Relationship to Study Treatment**

The investigator will assess causal relationship between Investigational Product (IP, which does not include Metformin) and each AE, and answer ‘yes’ or ‘no’ to the question “Do you consider that there is a reasonable possibility that the event may have been caused by the investigational product?”.

An AE with missing causal relationship will be considered related.

### **3.9.1.3 AEs Leading to Study Withdrawal/ Treatment Discontinuation**

AEs leading to study withdrawal and permanent discontinuation of study medication are AE records where “Study drug permanently discontinued due to this adverse event” is captured on “pAE” CRF page as the action taken with study medication. Since in this study, end of treatment is equivalent to end of study, they information can also be extracted from question “Does this AE cause patient’s withdrawal from study” on “pAE” CRF.

For AEs leading to discontinuation of study medication, summaries of incidence rates (frequencies and percentages) by SOC and PT will be prepared.

### **3.9.1.4 AEs Leading to Dose Adjustment or Interruption**

AEs leading to dose adjustment or interruption are AE records where “Study drug dosage adjusted/temporarily interrupted” is captured on “pAE” CRF page as the action taken with study medication.

For AEs leading to dose adjustment or interruption, summaries of incidence rates (frequencies and percentages) by SOC and PT will be prepared.

### **3.9.1.5 Serious AEs (SAEs)**

Serious adverse events (SAEs) are those events recorded as “Serious” on the “pAE” page of the CRF. A summary of serious AEs by SOC and PT will be prepared.

Criteria for SAEs can be found in protocol Section 6.2.

### **3.9.1.6 AEs Leading to Death**

AEs leading to death are those events with an outcome of “fatal”, on the “pAE” CRF page. A summary of AEs leading to death by SOC and PT will be prepared.

### 3.9.1.7 Hypoglycemic Events and Hypoglycemic AEs

Hypoglycemic AEs are captured on “pAE” page of the CRF, and identified using question “Is the Adverse Event a hypoglycemic event?”. Hypoglycemic AEs will be presented by SOC and PT.

Subjects reporting at least one episode of a hypoglycemic event, which is not necessarily an AE, and event frequency are collected on CRF page “pDIARYYN2”. Summary of incidence rates (event amount and percentages) will be prepared and corresponding 95% Clopper-Pearson exact confidence intervals (for the probability of a subject reporting at least 1 event) will be reported. A comparison between the treatment groups will be performed using two-sided Fisher’s exact test and resulting p-value will be reported.

$$H_0: \pi_T = \pi_C \text{ Versus } H_A: \pi_T \neq \pi_C$$

Where  $\pi_T$  denotes the probability of reporting a hypoglycemic event for subjects received Dapagliflozin (Treatment under investigation, T) and  $\pi_C$  denotes the probability of reporting a hypoglycemic event for subjects received Glimepiride (Comparator, C).

Frequencies of hypoglycemic events reported by each subject will be summarized and listed for SAF set.

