Drug accountability of investigational product and metformin will be conducted.

Investigational product and metformin will be dispensed.

In case of glimepiride group, glimepiride can be up titrated to 2 mg to maintain glycaemic control at the discretion of the investigator after evaluation of glycaemic control in subjects. Glimepiride can be also down titrated to mitigate recurrent hypoglycaemic events at the discretion of the investigator but 0mg is not allowed. If further hypoglycaemic events occur with meeting the discontinuation criteria after taking the 1mg glimepiride, subjects may be discontinued from investigational product.

All serious adverse events will be reported.

Adverse Events will be collected from subject actually taking the IP.

Subjects will discontinue the study if one major hypoglycaemic event or recurring minor hypoglycaemic events (any recurrent events of hypoglycaemia, as judged by the investigator, not meeting the definition of major hypoglycaemic event) occur.

Randomized subjects who discontinue the study prematurely should immediately stop taking investigational product and complete the procedures described for Visit 7.

4.4 End of Treatment: VISIT 7

Physical exam contains measurement of weight, waist circumflex, pulse and blood pressure. BMI calculation will be conducted.

12 lead ECG will be conducted.

Subjects will be followed for laboratory assessment of efficacy and safety according to study plan FBG, HbA1c, CBC, AST, ALT, total bilirubin, BUN, creatinine, electrolytes, total cholesterol, triglyceride, HDL-cholesterol, urinalysis, hsCRP, adiponectin. All laboratory assessment will be done in central laboratory.

Diet and life-style counselling will be given to the subject.

DXA and abdominal CT measurement will be conducted.

Concomitant medications will be checked.

Drug accountability of investigational product and metformin will be conducted.

Subject diary will be reviewed for hypoglycaemic events.

All serious adverse events and adverse events will be reported and followed up

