## 1.2 Study design

This is a 52 weeks, randomized, open-label, parallel-group, multi-centres phase IV study to evaluate the effects of Dapagliflozin compared with Glimepiride on body composition in patients with Type 2 Diabetes inadequately controlled with Metformin. 120 participants will be randomized 1:1 to receive Dapagliflozin 10 mg qd or Glimepiride 1~2 mg qd in an open-label manner for 12 months as add-on to Metformin 1000 mg. The study design and plan are summarized in Figure 1 below and Table 1 in study protocol.

Figure 1 Study Flow Chart

Scheduled visits of the study include measurements at baseline, 4, 12, 24, 36 and 52 weeks. Subjects with T2DM and inadequate glycaemic control ( $HbA1c \geq 7.5\%$  and  $\leq 9.5\%$ ) having stable Metformin monotherapy  $\geq 1000$  mg/day for at least 8 weeks prior to enrolment will be eligible to enter the study. Subjects early terminate or complete study treatment will not be further followed after End of Treatment (EoT) Visit. Table 1 in study protocol provides a detailed schedule of assessments of events related to the study objective.

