### **3.1 General Principles**

All safety outcome summaries will be performed on the SAF whilst all efficacy analyses will be performed on FAS or PPS (PPS for sensitivity analyses of efficacy endpoints) unless otherwise stated. In addition to the formal presentation of results detailed in the following sections, all study data will be listed by centre, patient number and treatment group.

For continuous data, descriptive statistics will be presented for each treatment group and overall, which includes number of patients (n), mean, SD, median, maximum and minimum unless otherwise specified.

For categorical data, the frequency and percentage of patients in each category will be presented. Counts that are zero will be displayed as “0” and all percentages will be based on population size of each treatment group unless otherwise specified.

Data will be listed to the same accuracy as recorded in the eCRF. Mean and median summary statistics will be presented to one additional decimal place, whilst the standard deviation (SD) will be presented to two additional decimal places. Minimum and maximum values will be presented to the same accuracy as recorded on the eCRF.

The default significant level of statistical testing will be 5%; confidence intervals will be two-sided 95% and all tests will be two-sided, unless otherwise specified in the description of the analyses.

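### Hypoglycaemic event counts are labelled incidence rates but have no observed-time denominator, although hypoglycaemia can itself end a subject's follow-up

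*SAP*

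**What the plan says.** SAP 3.9.1.7 plans two kinds of output from the hypoglycaemia diary page of the CRF.

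- **Subject level.** A Clopper-Pearson interval ("for the probability of a subject reporting at least 1 event) will be reported") and a test: "A comparison between the treatment groups will be performed using two-sided" Fisher's exact test. The tested parameter "denotes the probability of reporting a hypoglycemic event for subjects received Dapagliflozin", with the matching quantity for glimepiride.
- **Event level.** "Summary of incidence rates (event amount and percentages) will be prepared", and "Frequencies of hypoglycemic events reported by each subject will be summarized and listed for SAF set". No person-time is named. The general rule in SAP 3.1 is that "all percentages will be based on population size of each treatment group unless otherwise specified", so the denominator is the number of subjects in the arm.

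Three other provisions bear on how long events are observed.

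- Protocol 4.3: "Subjects will discontinue the study if one major hypoglycaemic event or recurring minor hypoglycaemic events" occur. Protocol 3.9 and 7.2, and another paragraph of 4.3, use *may* and refer to discontinuation of investigational product.
- SAP 1.2: "Subjects early terminate or complete study treatment will not be further followed after End of Treatment (EoT) Visit". SAP 3.9.1.3 treats end of treatment and end of study as the same thing.
- Protocol 5.2.3: events are recorded in a diary that is reviewed and transcribed at each visit, so recording stops at the exit visit.

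Protocol 2.3 lists number, frequency and proportion under the hypoglycaemia safety objective. SAP 3.6.1 derives days of exposure for each subject, but SAP 3.9.1.7 does not use them.

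**The concern.** An event count is comparable between arms only if the arms are observed for similar lengths of time. Here the outcome can shorten its own observation. A subject with repeated events may leave, and the remaining months contribute neither events nor any correction for lost time. The proportional loss is larger where events are more frequent. Protocol 1.1 names hypoglycaemia as a frequent sulfonylurea side effect, so that arm is expected to be glimepiride.

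A reader who sees two event totals in a table of incidence rates could take them as yearly frequencies. If event-driven exits are common, the totals would make the arms look closer than they are. The subject-level test does not fill this gap, because it addresses the proportion and not the frequency.

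**Working it through.** The plan states no hypoglycaemia rate or expected count, so there is no figure to reproduce. What follows is an illustration under assumptions.

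**Inputs from the documents:** 120 subjects randomised 1:1, so 60 per arm; 52 weeks of treatment, taken as one year.

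**Assumptions:** dapagliflozin 0.1 events per subject-year; glimepiride 0.5 or 1.0; certain exit at the *k*-th event; a constant rate within each subject. Rates either do not vary between subjects (Poisson) or follow a gamma distribution with shape *a* = 1 or 0.5. The smaller shape means more variation.

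**Formula.** If *N* is the number of events a subject would have in a full year, the number counted is min(*N*, *k*).

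- Exit at the 2nd event: E[min(*N*,2)] = 2 − 2P₀ − P₁
- Exit at the 3rd event: E[min(*N*,3)] = 3 − 3P₀ − 2P₁ − P₂
- Poisson with mean *m*: P₀ = e^(−m), P₁ = m·e^(−m), P₂ = m²·e^(−m)/2
- Gamma: P₀ = (a/(a+m))^a, P₁ = m·(a/(a+m))^(a+1), P₂ = [a(a+1)/2]·(m/(a+m))²·P₀

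The shortfall is 1 − E[min(*N*, *k*)]/*m*.

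**Exit at the 2nd event**

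| Rate per year | Variation | P₀ | P₁ | Counted per subject | Shortfall |
|---|---|---|---|---|---|
| 0.5 | Poisson | 0.6065 | 0.3033 | 0.4837 | 3.3% |
| 0.5 | a = 1 | 0.6667 | 0.2222 | 0.4444 | 11.1% |
| 0.5 | a = 0.5 | 0.7071 | 0.1768 | 0.4090 | 18.2% |
| 1.0 | Poisson | 0.3679 | 0.3679 | 0.8964 | 10.4% |
| 1.0 | a = 1 | 0.5000 | 0.2500 | 0.7500 | 25.0% |
| 1.0 | a = 0.5 | 0.5774 | 0.1925 | 0.6529 | 34.7% |
| 0.1 | Poisson | 0.9048 | 0.0905 | 0.0998 | 0.2% |
| 0.1 | a = 1 | 0.9091 | 0.0826 | 0.0992 | 0.8% |
| 0.1 | a = 0.5 | 0.9129 | 0.0761 | 0.0982 | 1.8% |

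With 60 glimepiride subjects at 1.0 per year, full follow-up gives 60 events. The counted numbers are 60 × 0.8964 = 53.8, 60 × 0.75 = 45 and 60 × 0.6529 = 39.2. Against dapagliflozin at 0.1 per year, the ratio of counts is 8.98, 7.56 or 6.65 where the ratio of rates is 10.

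**Exit at the 3rd event, 1.0 per year**

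- Poisson (P₂ = 0.1839): 0.977 counted, shortfall 2.3%
- a = 1 (P₂ = 0.125): 0.875 counted, shortfall 12.5%
- a = 0.5 (P₂ = 0.0962): 0.787 counted, shortfall 21.3%

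**Discretionary exit.** In simulation at 1.0 per year, a 50% chance of leaving at each event from the second onward loses 5.9% (Poisson) to 24.9% (a = 0.5). A 25% chance loses 3.0% to 16.2%.

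**The tested quantity.** Exit under this rule needs a prior event, so P(*N* ≥ 1) does not change. Under Poisson it is 1 − e^(−0.1) = 0.095 and 1 − e^(−1) = 0.632, with or without the rule.

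**What a time denominator recovers** (1.0 against 0.1 per year, exit at the 2nd event, true ratio 10). Under Poisson, crude events per person-year return 10. With gamma variation, simulation gives about 7.5 to 8.5 for crude person-years and about 9.9 to 10.0 for a negative binomial model with log-time offset. The last result comes from data generated by that same model.

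**The case against.** **No comparison of event amounts is planned.** This is correct. The only test is on subjects with at least one event, and Protocol 8.5.2 plans the same. A reader might infer that the formal hypoglycaemia comparison is biased by the exit rule. The documents do not support that, because everyone who leaves under the rule already counts as having had an event. Exits for other reasons can still make follow-up unequal, but that is a separate matter.

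**Under-counting is not certain.** This also stands. Protocol 4.3 says *will* in one paragraph and *may* in another; 3.9 and 7.2 say *may*; recurrence is left to the investigator; glimepiride can be down-titrated. Protocol 5.2.3 asks a subject with more than one minor event since the last visit to contact the investigator and does not mention exit. Several events can accumulate between visits. Exit at exactly the second or third event is therefore a strong assumption. The events lost are also hypothetical ones on continued treatment at an unchanged rate, not observed events left out.

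**Incidence rate may only mean counts and percentages.** SAP 3.9.1.3 and 3.9.1.4 use the term for ordinary frequency tables, and no per-year figure is promised. So the plan cannot be said to treat every subject as observed for 52 weeks. Exposure days and discontinuation reasons are reported elsewhere, so a careful reader could see unequal follow-up. Even so, the per-subject event frequencies are clearly planned, and nothing connects them to observed time.

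**The correction depends on a model.** Crude person-time corrects only part of the truncation when event-prone subjects leave early. The offset model relies on gamma-type variation and on rates that do not change with down-titration. This is a reason to label the estimate descriptive, not to omit it.

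**Conclusion.** The point holds as a minor weakness in a descriptive safety summary. Event amounts and per-subject frequencies are set side by side with no observed-time denominator, while hypoglycaemia can end follow-up, so they may understate the difference between arms. It is not an error in the planned test.

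The size is unknown from the documents. With certain exit at the second event, the glimepiride shortfall is about 3% to 18% at an assumed 0.5 events per year and about 10% to 35% at 1.0. With exit at the third event at 1.0 per year it is about 2% to 21%. The dapagliflozin shortfall, with exit at the second event at an assumed 0.1 per year, is under 2%. These figures rest on assumed rates, assumed variation between subjects and a fixed exit threshold. Discretionary exit or down-titration would change them. The direction rests on the protocol's qualitative expectation of more hypoglycaemia on the sulfonylurea.

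**What to change.** In SAP 3.9.1.7:

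1. Derive observed time for each subject, from first dose to the last diary review or exit visit. If diary-review dates are not available, use the exposure days of SAP 3.6.1, which rest on administration dates.
2. Report total observed time and events per patient-year by arm, with a rate ratio and 95% CI from a negative binomial model with treatment as factor and log(observed time) as offset. Label it descriptive.
3. If the model does not converge, report crude events per patient-year with exact Poisson intervals. State that crude person-time corrects only part of the truncation and that these intervals ignore variation between subjects.
4. Report the number of hypoglycaemia-related exits per arm, and footnote the raw counts as truncated by exit.
5. Keep the proportion, Clopper-Pearson interval and Fisher's test unchanged.

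The *will* and *may* discontinuation passages in Protocol 3.9, 4.3 and 7.2 must be reconciled; no clinical rule is proposed here.

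The cost is SAP wording, one descriptive table and one model. With the fallback to exposure days, no new data are needed. The interval will be wide if events are few: at the assumed 0.1 per year, dapagliflozin would have about 60 × 0.1 = 6 events.

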### 3.9.2 Deaths

If any patient dies during the study, relevant information will be captured on CRF page “pAE” as a SAE.

Incidences and percentages of death and will be summarized and listed.

### 3.9.3 Laboratory Evaluations

Results from the central laboratory will be included in the reporting for serum chemistry, hematology and urinalysis. A list of tests to be performed is included in Protocol section 5.2.1.

The following summaries will be provided for laboratory data:

- Actual value of each scheduled visit and change from baseline for each post-baseline scheduled measurement by visit (for quantitative measurements only).
- Incidence of abnormal values according to normal range criteria. Abnormalities will be classified to “Low” if smaller than the lower limit while “High” if larger than the upper limit.
- Shift from baseline according to abnormality status (Low, Normal and High) for each post-baseline scheduled measurement. For urinalysis, shift between normal and abnormal will be prepared.
- Listing of observed results for all laboratory values will be provided with abnormality status flagged.

- Additionally, Change from screening (visit 1) to each post-treatment time point will be reported for CBC, electrolytes, lipid parameters.

### **3.9.4 ECG Evaluations**

ECG results will be captured on CRF page “pECG” and will contain overall assessment based on Investigator’s judgment:

- Normal
- Abnormal, Not Clinically Significant (ANCS)
- Abnormal, Clinically Significant (ACS)

For baseline and each post-baseline measurement, the numbers and percentages of patients in each category above will be summarized.

In addition, heart rate, PR interval, QRS interval and QT interval will be summarized and listed for SAF set.

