Demography, medical/surgical and diabetes history will be checked, 12 lead ECG will be conducted.

Physical exam will be conducted.

Height will be measured in cm (without shoes), weight in kg (light clothes and without shoes) and waist circumference (in cm). BMI calculation will be conducted. Pulse and blood pressure (SBP, DBP) will be measured.

Laboratory baseline test for efficacy and safety parameters will be conducted: FBG, HbA1c, CBC, AST, ALT, total bilirubin, BUN, creatinine, electrolytes, total cholesterol, triglyceride, HDL-cholesterol, urinalysis, hsCRP, adiponectin. All laboratory assessment will be done in central laboratory. Pregnancy test by dipstick should be performed for all WOCBP.

All serious adverse events occurring after signing the informed consent will be reported.

Concomitant diabetes and other medications will be checked.

Eligible patients will receive an enrolment code.

4.2 Randomization: VISIT 2

Eligibility criteria will be checked.

Subjects will be randomized to the treatment arm. Subjects who do not meet these criteria must not be randomized in the study.

DXA and abdominal CT baseline measurement will be conducted.

Diet and life-style counselling will be given to the subject.

Subjects will be given a diary to record hypoglycaemic events (symptoms).

All subjects will be instructed to constantly follow hygiene to avoid urinary tract infections.

Study drug will be dispensed according to randomisation. 1mg glimepiride will be dispensed first to the subjects who are allocated to glimepiride group. Metformin will be dispensed.

All serious adverse events will be reported.

Adverse Events will be collected from subject actually taking the IP.

4.3 Treatment Period: VISITS 3, 4, 5, 6

Physical exam contains measurement of weight, waist circumflex, pulse and blood pressure. BMI calculation will be conducted.

Subject diary will be reviewed for hypoglycaemic events. New diary will be dispensed to the subjects.

Subjects will be followed for laboratory assessment of efficacy and safety according to study plan:

- Visit 3: FBG, urinalysis
- Visit 4: FBG, HbA1c, AST, ALT, total bilirubin, BUN, creatinine, urinalysis
- Visit 5: FBG, HbA1c, CBC, AST, ALT, total bilirubin, BUN, creatinine, electrolytes, urinalysis
- Visit 6 : FBG, HbA1c, urinalysis

All laboratory assessment will be done in central laboratory.

Diet and life-style counselling will be given to the subject.

Concomitant medications will be checked.

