5.2 Safety assessments

5.2.1 Laboratory safety assessments

Blood sample for laboratory measurement will be performed at central laboratory.

Table 2 Laboratory Safety Variables

Haematology/Haemostasis (whole blood)	Clinical Chemistry (serum or plasma)
B-Haemoglobin (Hb)	S/P-Creatinine
B-Leukocyte count	S/P-Bilirubin, total
B-Leukocyte differential count (absolute count)	S/P-Alkaline phosphatase (ALP)
B-Platelet count	S/P-Aspartate transaminase (AST)
	S/P-Alanine transaminase (ALT)
Urinalysis (dipstick)	S/P-Albumin
U-Hb/Erythrocytes/Blood	S/P-Potassium
U-Protein/Albumin	S/P-Calcium, total
U-Glucose	S/P-Sodium
	S/P-Creatine kinase (CK)

5.2.2 12-Lead ECG

A 12-lead ECG will be taken (supine position, standard ECG with a recommended paper speed of 50 mm/second covering at least 6 sequential beats) after the subject has been lying down resting for at least 5 minutes. The ECG will be evaluated by the investigator and entered as “Normal” or “Abnormal” in the eCRF. If the ECG is evaluated as “Abnormal” the abnormality should be further specified.

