8.4 Outcome measures for analyses

Efficacy Variables

- Change from Baseline: Change from baseline will be calculated as absolute difference between the values measured at a specific time point after baseline minus baseline value. Baseline value is defined to be Visit 2 (randomization).
- Proportion of subjects achieving a glycemic response, defined as HbA1c < 7.0% at Week 52.

If no measurements is available at Week 52, the last post-baseline HbA1c prior to Week 52 will be used instead for analysis.

Safety Variables

The following safety data will be collected: CBC, electrolytes, lipid, urinalysis, vital signs (pulse), reported hypoglycemic events and adverse events.

Change from screening (Visit 1) to each post-treatment time point where scheduled assessments were made will be calculated for CBC, electrolytes, lipid, and vital signs (pulse).

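### SAP 3.9.4 tabulates heart rate and uncorrected QT separately and derives no rate-corrected QT, so the QT summary cannot by itself be read as a repolarisation signal

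*SAP*

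**What the plan says.** Protocol 5.2.2 sets out the recording: "A 12-lead ECG will be taken", supine and after rest. "The ECG will be evaluated by the investigator and entered as" either normal or abnormal, with any abnormality specified. It asks for no interval and gives no correction method.

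The ECG is scheduled twice. At screening (Protocol 4.1): "Demography, medical/surgical and diabetes history will be checked, 12 lead ECG will be conducted". At the end-of-treatment visit (Protocol 4.4): "12 lead ECG will be conducted".

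SAP 3.9.4 plans two outputs. The first is the investigator's overall judgement in three categories (normal; abnormal, not clinically significant; abnormal, clinically significant): "For baseline and each post-baseline measurement, the numbers and percentages of patients in each category above will be summarized". The second is the set of measured intervals: "In addition, heart rate, PR interval, QRS interval and QT interval will be summarized and listed for SAF set". QTc, RR, Fridericia and Bazett appear in neither document, including the abbreviation lists. SAP 3.9.3 and 3.9.5 ask for change from baseline for laboratory values and vital signs; SAP 3.9.4 does not ask for it for the ECG intervals.

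SAP 3.9 fixes the status of all this: "There will be no statistical comparison between treatment groups for safety data except hypoglycemic events". The protocol's list of safety variables (8.4) does not name ECG: "The following safety data will be collected: CBC, electrolytes, lipid, urinalysis, vital signs (pulse), reported hypoglycemic events and adverse events".

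**The concern.** The QT interval depends on heart rate: the faster the heart, the shorter the QT, even when repolarisation is unchanged. A table of mean QT at screening and at Week 52, by arm, therefore carries two effects at once. If mean heart rate differs between visits or between arms, raw QT can move with no change in repolarisation, or stay still while the corrected interval lengthens. The second case matters more for safety, because the table would then look reassuring.

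Heart rate is summarised in the same sentence, but as a separate variable. The correction is non-linear and applies to each ECG, so group summaries of heart rate and of QT do not give the mean, spread or individual change of the corrected interval. What is at stake is how one descriptive safety table reads. No test, analysis set or efficacy result depends on it.

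**Working it through.** The documents state no QT value, threshold or precision for ECG, so there is no figure of the plan's own to reproduce. The check is an illustration of how strongly raw QT depends on heart rate.

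**Inputs**
- From the documents: the variables summarised (heart rate, PR, QRS, QT; SAP 3.9.4), and the two ECG time points (Protocol 4.1 and 4.4).
- Assumed, not in the documents: a true QTcF of 400 ms, a starting heart rate of 60 to 80 bpm, and a mean rise of 5 bpm.

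**Formula (Fridericia)**
- QTcF = QT / (60/HR)^(1/3), so QT = QTcF × (60/HR)^(1/3).

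**Step 1: repolarisation constant, heart rate rises**
- At 70 bpm: 400 × (60/70)^(1/3) = 379.97 ms.
- At 75 bpm: 400 × (60/75)^(1/3) = 371.33 ms.
- Difference: 371.33 − 379.97 = −8.6 ms, all of it due to heart rate.

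**Step 2: raw QT constant, heart rate rises**
- With raw QT still 379.97 ms at 75 bpm, QTcF = 379.97 / (60/75)^(1/3) = 409.3 ms.
- The QTcF rise that raw QT does not show is 409.3 − 400 = 9.3 ms.

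**Step 3: range over starting heart rate, each for a 5 bpm rise**

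| Starting rate (bpm) | Raw QT shift at constant QTcF (ms) | QTcF rise hidden at constant raw QT (ms) |
|---|---|---|
| 60 | −10.5 | 10.8 |
| 70 | −8.6 | 9.3 |
| 80 | −7.3 | 8.2 |

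For a shift of only 1 bpm in either direction, raw QT moves by about 1.5 to 2.2 ms over the same range of starting rates.

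**Step 4: dependence on the assumptions**
- With QTcF at 420 ms, the 70 to 75 bpm shift is −9.1 ms, so the assumed level matters little.
- With Bazett's square-root formula at 400 ms, the same shift is −12.6 ms (−15.7 to −10.3 ms for starting rates of 60 to 80 bpm). The size therefore depends on the formula, which is a reason to name one in advance.

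**Step 5: after the fix**
- In the setting of step 1, QTcF at 75 bpm is 371.33 / (60/75)^(1/3) = 400.0 ms, a change of 0 ms.
- In the setting of step 2, the 9.3 ms rise appears in the table.

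**The case against.** The strongest reply is that little rests on this output. ECG is in neither the safety objective's outcome measures (Protocol 2.3) nor the list of safety variables (Protocol 8.4). It is not compared statistically between arms, and the investigator's category is tabulated whatever happens to the QT row. Heart rate is shown beside QT, and sitting pulse with its change from baseline is summarised separately (SAP 3.9.5), so a reader would see a heart-rate shift. Both ECG values are listed, so a corrected QT could be calculated later. All of this stands, and it keeps the point minor. It does not remove it: the investigator's category cannot show a mean shift in an interval, and a correction made later would use a formula chosen after the data are seen.

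A second reply is that the distortion is hypothetical. This also stands. With 120 subjects randomised 1:1, about 60 per arm, chance alone would not produce much of it. If heart rate varied with an assumed SD of 6 to 10 bpm around 72 bpm, it would add an SD of about 10.6 to 18.0 ms to raw QT. The resulting standard error of a between-arm mean difference at one visit is SD × √(2/60), or 1.9 to 3.3 ms. A systematic distortion of 8 to 9 ms would need a real mean heart-rate difference of about 5 bpm, and nothing in the documents points to one.

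A reader might infer that the QT summary cannot be interpreted at all, or that the ECG data can support no safety conclusion. The documents do not support that. Heart rate is reported alongside, the listings allow recalculation, and the clinical category stands on its own. What holds is narrower: raw QT alone does not separate repolarisation from heart rate.

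**Conclusion.** The point holds in this limited form. SAP 3.9.4 specifies only uncorrected QT, and a rate-corrected interval would be the better descriptive summary. For a 5 bpm rise the illustrative size is a raw QT shift of about −7 to −11 ms with no change in repolarisation, or a hidden QTcF increase of about 8 to 11 ms. These figures rest on an assumed QTcF of 400 ms, starting rates of 60 to 80 bpm and the Fridericia formula. They are not an estimate of bias in this trial.

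Protocol 5.2.2 does not conflict with the SAP here; it simply does not address intervals. The primary analysis, the secondary efficacy analyses and the tested safety comparison (hypoglycaemic events) are unaffected. This is an optional improvement at almost no cost.

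**What to change.** In SAP 3.9.4, add a derivation for each ECG: QTcF = QT / (60/heart rate)^(1/3). Summarise QTcF, and its change from baseline to Week 52 or end of treatment, by arm for the safety set. Use the baseline rule in SAP 3.1.1 and the early-termination rule in SAP 3.1.3. Keep raw QT and heart rate in the same table, and list all three. Raw QT need not be removed. Fridericia is a reasonable choice, but what matters most is that one formula is named before the data are summarised.

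The cost is one derived variable and one or two table rows, with no new visit, procedure or data. This assumes that QT and heart rate come from the same ECG, as SAP 3.9.4 implies; the case report form is not among the documents, so the sponsor should confirm it.
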